Data analysis:	
For the incident users of Jardiance® (Empagliflozin) and of DPP4i, analysis will be performed using the “as-treated” (AT) approach. This corresponds to censoring individuals who discontinue use of the index drug, i.e. either switch from the index drug to any other of the index drug Jardiance® (Empagliflozin) or DPP-4 inhibitor during follow-up or stop using the index drug.
 
For the assessment of the primary and secondary objectives, the main data analysis will be conducted in two stages:
 
 - Construction of the propensity score (PS) by modelling the exposure Jardiance® (Empagliflozin) vs. DPP-4 inhibitor - Estimation of the effect of exposure to Jardiance® (Empagliflozin) on the ketoacidosis, severe urinary tract infections, volume depletion and dehydration compared to those exposed to DPP-4 inhibitor. 
Additional sensitivity analyses will be performed to validate the robustness of alternative definitions of outcome, exposure, covariates and reduction of bias due to matching.
 
The following estimates and comparison will be generated:
 
 - Crude and adjusted incidence rates of each of the outcomes among Jardiance® (Empagliflozin) new users and among DPP-4 inhibitor new users. Incidence rates will be reported as point estimates (in cases per 1,000 person-years) and 95% confidence intervals (CIs). - Summary IRRs, after adjusting (via stratified Mantel-Haenszel analysis) for propensity score deciles and calendar year, among Empagliflozin new users versus DPP-4 inhibitor new users - Adjusted IRRs for each of the outcomes will be the main effect estimates of interest. Adjusted incidence rates and IRRs will be calculated by weighting the incidence or IRR of each stratum (defined by propensity score decile and calendar year) by the amount of Jardiance® (Empagliflozin) person-time within the stratum - An additional analysis will further stratify the IRRs by categories of insulin use at the index date - Additional sensitivity analyses will be performed to evaluate potential for bias and confounding. 		

Name of company: [REDACTED]			
Name of finished medicinal product: Jardiance®			
Name of active ingredient: Empagliflozin			
Protocol date: 16 Oct 2017	Study number: 1245.149	Version/Revision: 3.0	Version/Revision date: 23 Sep 2019

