7. RATIONALE AND BACKGROUND

Around 415 million patients are affected by DM worldwide. DM is considered an epidemic in many countries of the world, and the number of people affected is expected to double over the next decade. [R16-4703] DM is a major leading cause of many complications and diseases such as heart diseases and several types of infections. T2DM is more common than type 1, comprising 90-95% of all DM cases. [R17-3422] Over 5 million people died from DM in 2015 worldwide. In the Middle East and North Africa, around 36 million patients were affected by DM in 2015, a number expected to rise to 72 million patients by 2040. Saudi Arabia has one of the highest prevalence of DM in the world with over 20% of the population affected. [R16-4703]

Empagliflozin is a selective sodium/glucose co-transporter 2 (SGLT2) inhibitors one of the most recent classes of drugs used to treat T2DM. SGLT2 inhibitors promote the renal excretion of glucose and help lower elevated blood glucose levels in patients with T2DM. [P14-06594] In Saudi Arabia, It is indicated for treatment of T2DM as monotherapy or add-on combination therapy. It is used as monotherapy when exercise and diet control alone do not provide glycaemic control in patients for whom use of metformin is considered inappropriate because of intolerance. It is also used in combination with other glucose lowering agents—including insulin—when they do not provide adequate glycaemic control. [R17-3413] Several clinical trials showed the efficacy of Empagliflozin in reducing the blood glucose level. Furthermore, Empagliflozin is a unique drug among all hypoglycaemic agents because it has shown a reduction in major cardiovascular events, which has not been the case with other oral hypoglycaemic agents. Empagliflozin, as other SGLT2 inhibitors, is associated with some adverse reactions such as urinary tract infections and genital infections, especially in females. In addition, rare cases of diabetic ketoacidosis (DKA) have been reported. [P15-03461], [P13-09179], [P15-05613] In parallel to the launch of SGLT2 inhibitors in Saudi Arabia, the Saudi Food and Drug Authority (SFDA) has requested a non-interventional study to further monitor the safety of Empagliflozin in the country, including during the Ramadan period.

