9.7.2 Main analysis using stratification

For the incident users of Empagliflozin along with their respective comparators, analysis will be performed using the “as-treated” (AT) approach. This corresponds to censoring individuals who discontinue use of the index drug, i.e. who either switch from the index drug to any other of the index drugs (Empagliflozin or DPP-4 inhibitor) during follow-up or who stop using the index drug. The AT approach is considering index periods.

For each event of interest, ketoacidosis, severe urinary tract infections, volume depletion, and dehydration, crude and adjusted incidence rates per cohort will be described and compared by means of incidence rate ratios (IRR). Incidence rates will be reported as point estimates and 95% confidence intervals (CIs). Crude incidence rates will be adjusted per 1,000 person-years. Per cohort and, where appropriate per stratum and/or subgroup, the number of person-years is the sum of length of index periods of all patients. Time to first event occurrence will be compared by means of hazard ratios and their 95% confidence intervals.

IRRs and hazard ratios are analysed using stratification. Strata are defined by PS quintiles. IRRs are investigated by means of a stratified Mantel-Haenszel analysis, while hazard ratios are investigated by means of a Cox regression, if proportional hazards can be assumed.

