4.9.1 Analysis of Primary Endpoints

For each of the four target adverse events (DKA, volume depletion, dehydration, serious UTI) the primary endpoints are the incidence rates and times to first occurrence in the index period,

Statistical Analysis Plan (SAP)

Document Date: 17APR2019

Document Version: 1.0 Final

analysed within each PS-based stratum by logistic regression and proportional-hazards Cox regression, respectively. Time to first event occurrence will be compared using hazard ratios and their 95% confidence limits. The assumption of proportional hazards will be tested [Kleinbaum 2012].

Estimates for each stratum and respective variances will be averaged across strata to yield overall weighted estimates considering subclass weights [Austin 2010, Guo 2015].

The statistical analysis models will contain factors and covariates with a potential effect on the outcome. These may include the treatment-confounding candidates listed in section 4.9 above, and will include the season, i.e., the quarter of the calendar year of the index date, and other effects yet to be short-listed. Site may also be included as a candidate variable.

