4.9.2 Analysis of Secondary Endpoints

Secondary endpoints are the same as primary endpoints but in the index period during Ramadan. They are analyzed like the primary endpoints.

Statistical Analysis Plan (SAP)

Document Date: 17APR2019

Document Version: 1.0 Final

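### Every readable between-group measure is a ratio to DPP-4 inhibitor, with no finite value if that group has no event; the SAP's averaging across strata can fail sooner, and no sparse-event method is stated

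*Protocol*

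**What the plan says.** - **Main measure.** Under protocol 9.7.2, crude and adjusted incidence rates "will be described and compared by means of incidence rate ratios (IRR"), using a stratified Mantel-Haenszel analysis over PS quintiles. The abstract fixes the status of this measure: "Adjusted IRRs for each of the outcomes will be the main effect estimates of interest".
- **Second measure.** Protocol 9.7.2 also states: "Time to first event occurrence will be compared by means of hazard ratios and their 95% confidence intervals". SAP 4.9.1 repeats this: "Time to first event occurrence will be compared using hazard ratios and their 95% confidence limits".
- **SAP models.** Incidence rates and times to first event are to be "analysed within each PS-based stratum by logistic regression and proportional-hazards Cox regression, respectively". Then: "Estimates for each stratum and respective variances will be averaged across strata to yield overall weighted estimates", using subclass weights. SAP 4.10 also keeps the Mantel-Haenszel analysis.
- **Direction.** SAP 4.7.5 puts DPP-4 inhibitor in the denominator of the ratios.
- **Ramadan.** SAP 4.9.2 says of the secondary endpoints: "They are analyzed like the primary endpoints".
- **Absolute quantities.** Both documents plan incidence rates per group with 95% CIs and Kaplan-Meier estimates. The abstract also plans adjusted rates per group. No readable text or table title names a rate or risk difference between groups, an exact interval, or a rule for zero events.
- **Expected counts.** None is given. Protocol 7 says only that "rare cases of diabetic ketoacidosis (DKA) have been reported", and protocol 9.9 warns that numbers may be low for assessing DKA.

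**The concern.** A ratio with a zero denominator has no finite estimate. The Mantel-Haenszel IRR has a zero denominator when the comparator has no event in any stratum; in the same case the Cox and logistic estimates diverge. The method in SAP 4.9.1 is more fragile. It needs a usable estimate from every stratum, so one stratum with events in only one arm, or in neither, leaves the weighted average undefined. Subclass weights based on stratum size would not down-weight such a stratum.

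Protocol 9.5 ties the 750 patients per group to detecting DKA. If cases occur on empagliflozin and none on DPP-4 inhibitor, the main effect estimate has no value in the very pattern a safety study most needs to quantify. A method chosen after that result is seen would be open to criticism as post hoc.

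**Working it through.** **Inputs.** There are 750 patients per group (protocol 9.5), followed for 12 months (protocol 9), so at most 750 PY per group. Protocol 8.2 sets Ramadan at 29 days: 750 × 29/365.25 = 59.5 PY, if every patient stays on treatment through one Ramadan. SAP 4.4 ends Ramadan 2019 on 6 June; counted from 5 May that is 33 days, or 67.8 PY. There are five PS strata, so about 150 comparator PY each if balanced. The documents state no event rate, expected count or power, so there is no figure of theirs to reproduce. All rates below are assumptions shown as a range.

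**1. No comparator event at all.** P = exp(−rate × PY).

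| Comparator rate per 1,000 PY | 750 PY | 600 PY (assumed loss to as-treated censoring) |
|---|---|---|
| 0.5 | exp(−0.375) = 69% | 74% |
| 1 | exp(−0.75) = 47% | 55% |
| 2 | exp(−1.5) = 22% | 30% |
| 4 | exp(−3) = 5% | 9% |

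P exceeds 50% only below ln 2/750 = 0.92 per 1,000 PY.

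In Ramadan (59.5 PY), P is 94% at 1, 55% at 10 and 23% at 25 per 1,000 PY. It exceeds 50% below 11.6 per 1,000 PY (10.2 with 33 days; 15.5 with 29 days and 25% of person-time lost).

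**2. At least one quintile with no comparator event, 12 months.** P = 1 − (1 − exp(−150 × rate/1,000))^5.

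- At 5 per 1,000 PY: 1 − (1 − 0.472)^5 = 96%. No comparator event overall has probability only 2% at that rate.
- At 10 per 1,000 PY: 1 − (1 − 0.223)^5 = 72%, against less than 0.1% overall.
- At 20 per 1,000 PY: 23%.

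In Ramadan (about 11.9 comparator PY per quintile) it is above 99.9% at every rate from 1 to 20 per 1,000 PY.

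**3. What can still be estimated** (illustrative counts, equal person-time, unstratified).

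- Exact conditional lower limit for the IRR at a v 0: p = 0.025^(1/a), limit = p/(1 − p). At 6 v 0: 0.541/0.459 = 1.18. At 5 v 0: 0.478/0.522 = 0.92. The upper limit is infinite.
- Rate difference with score 95% CI: the limits d solve (a/T − b/T − d)/√(r₁/T + r₂/T) = ±1.96, with r₁ and r₂ the maximum likelihood rates under difference d. At 5 v 0 over 750 PY it is 6.7 per 1,000 PY (1.5 to 15.6). At 3 v 0 it is 4.0 (−1.1 to 11.8). At 1 v 0 in Ramadan it is 16.8 (−47.7 to 95.1).
- At 0 v 0 the score limits are ±1.96²/T: ±5.1 per 1,000 PY at 750 PY and ±64.5 at 59.5 PY. A Wald interval has zero variance there and collapses to a point. At 1 per 1,000 PY in both groups, 0 v 0 in Ramadan has probability exp(−0.119) = 89%.
- Exact Poisson upper limit for a group with no event: 3.689/T, which is 4.9 per 1,000 PY over 12 months and 61.9 in Ramadan.

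**The case against.** Four points on the other side have weight.

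**The group comparison is not empty.** Per-group rates and Kaplan-Meier estimates with CIs are planned. The adjusted rates in the abstract are absolute, PS-standardised and finite at zero events. SAP 4.6 plans two-sided tests, and a Mantel-Haenszel score test works with one empty arm: at 6 v 0 with equal person-time, (6 − 3)²/(6 × 0.25) = 6.0, p = 0.014. So a reader who inferred that the study could end with no comparative information would go too far. What stands is that a test gives no effect size and two separate rates give no interval for their difference.

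**The list of measures may be incomplete.** Text after protocol 9.7.2, SAP 4.9.3 and part of SAP 4.10 are not readable. A claim that ratios are the only planned measures holds for the readable text alone. The readable table titles support it: the stratified analyses listed for each outcome are IRR or proportional-hazards analyses.

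**The interval method is unstated.** Neither document says how the CIs are calculated, so exact intervals are not ruled out. The fair criticism is that no method for sparse events is specified.

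**Zero events may not be likely.** A reader might infer from the word rare that no comparator ketoacidosis is the expected result, or that most outcomes will be empty in Ramadan. The documents do not support either. The remark on rare cases concerns SGLT2 inhibitors, not DPP-4 inhibitors, and no rate is given for any outcome. The only frequency, about 25% in protocol 9.5, covers urinary tract infection and other risk factors, not pyelonephritis or urosepsis. Read as a yearly rate it would give about 15 comparator events in Ramadan.

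**Conclusion.** The concern holds, limited to the readable text and conditional on assumed rates. Every readable between-group effect measure is a ratio that has no finite value without comparator events, and no difference or sparse-event method is stated.

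For complete absence of comparator events, the risk over 12 months runs from 69% at 0.5 to 5% at 4 per 1,000 PY. Even the 22% at 2 per 1,000 PY justifies a pre-specified answer. The more probable failure is in SAP 4.9.1: averaging breaks down when one stratum lacks events in one arm, with probability about 96% at 5 and 72% at 10 per 1,000 PY over 12 months. At those rates the Mantel-Haenszel IRR would almost always have a non-zero denominator.

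The figures assume Poisson counts, a constant rate, balanced quintiles and full person-time unless stated. Lost person-time raises the chance of zero events. This is a cheap improvement to an analysis that otherwise may not return its main estimate.

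**What to change.** In protocol 9.7.2 and SAP 4.9.1 and 4.9.2, for each outcome and each window:

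1. Add the PS-stratified difference in incidence rates per 1,000 PY, with the stratum weights named and a score-type 95% CI. Do not use a Wald interval, because of its collapse at 0 v 0.
2. Use exact Poisson CIs for the crude rate in each group.
3. When event counts are small (threshold stated in advance) or any stratum lacks events in one arm, estimate the IRR by the pooled Mantel-Haenszel or stratified exact conditional method with an exact 95% CI, in place of averaging stratum-specific estimates. With no comparator event at all, report the IRR as having no finite estimate, with its exact lower limit; at 0 v 0, report it as not estimable.
4. State that the IRR remains the main estimate and the rate difference is supportive. The two can disagree: at 5 v 0 the exact IRR lower limit is 0.92, while the score interval for the difference, 1.5 to 15.6 per 1,000 PY, excludes zero.

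The cost is a few lines of SAP text, standard procedures, one extra column per table and wider intervals. No further data are needed. In Ramadan the difference will be finite but very imprecise, and the report should say so.

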9.8 QUALITY CONTROL

All entries in the e-CRF and the existing coding will be stored in a database. The structure of the database is based on the division into sections and entry fields defined in the e-CRF. To improve and ensure data quality, data checks will be performed automatically in the e-CRF directly on electronic entry at the study site.

Plausible value ranges for numerical data entries and logical data and list entries will be filed in the e-CRF. The tests for consistency and completeness based on this will be performed during entry in the e-CRF. The validity of the recorded data will therefore be ensured by the validations incorporated in the documentation system, which highlight incorrect or implausible entries to the data entry clerk/doctor.

If corrections are necessary after the data are saved, these will be documented in an audit trail.

For the further quality assurance of the documented patient observations, a sample-based source data comparison will be performed on about 10% of the sites. An additional inspection/quality assurance check of this PASS can be performed in case of any deviation.

9.9 LIMITATIONS OF THE RESEARCH METHODS

There are several methodological challenges when conducting epidemiologic studies to evaluate the association between glucose-lowering medications and outcomes of interest among patients with diabetes. These challenges include, but are not limited to, changes in treatment in response to advancing diabetes or due to adverse effects of specific drugs and time-varying risk of an outcome depending on duration of exposure

Another limitation is that, the number of patients may be low to assess the risk of DKA.

Some patients may discontinue the study before Ramadan period and will not contribute to the assessment of the safety during this period.

9.10 OTHER ASPECTS

9.10.1 Data quality assurance

A quality assurance audit/inspection of this study may be conducted by the sponsor or sponsor's designees or by Institutional Review Board (IRBs) / Independent Ethics Committee (IECs) or by regulatory authorities. The quality assurance auditor will have access to all medical records, the investigator's study-related files and correspondence, and the informed consent documentation of this study.

9.10.2 Study records

Case Report Forms (e-CRFs) for individual patients will be provided by the sponsor, either on paper or via remote data capture.

9.10.2.1 Source documents

Source documents provide evidence for the existence of the patient and substantiate the integrity of the data collected. Source documents are filed at the investigator's site.

Data reported on the e-CRFs that are transcribed from source documents must be consistent with the source documents or the discrepancies must be explained. The investigator may need to request previous medical records or transfer records, depending on the study; also current medical records must be available.

For paper e-CRFs, the following data need to be derived from source documents:

- Patient identification (gender, date of birth)
- Patient participation in the study (substance, study number, patient number, date patient was informed)
- Dates of Patient's visits, including prescription of study medication
- Medical history (including study indication and concomitant diseases, if applicable)
- Medication history
- Adverse events and outcome events (onset date (mandatory), and end date (if available))
- Serious adverse events (SAEs) (onset date (mandatory), and end date (if available))
- Concomitant therapy (start date, changes)
- Originals or copies of laboratory results (in validated electronic format, if available)
- Conclusion of Patient's Participation in the study

9.10.2.2 Direct access to source data and documents

The investigator / institution will permit study-related monitoring, audits, IRB / IEC review and regulatory inspection, providing direct access to all related source data / documents. e-CRFs and all source documents, including progress notes and copies of laboratory and medical test results must be available at all times for review by the sponsor's clinical study monitor, auditor and inspection by health authorities (e.g. US Food and Drug Administration (FDA)). The Clinical Research Associate (CRA) / Clinical Monitor Local (CML) and auditor may review all e-CRFs and written informed consents. The accuracy of the data will be verified by reviewing the documents described in Section 9.10.2.1.

10. PROTECTION OF HUMAN SUBJECTS

The study will be carried out in compliance with the protocol, the principles laid down in the Declaration of Helsinki, in accordance with the ICH Harmonized Tripartite Guideline for Good Clinical Practice (GCP) (to the extent applicable to the NIS setting and required by local regulations), Good Epidemiological Practice (GEP), Guidelines for Good Pharmacoepidemiology Practice (GPP), and relevant BI and/or CRO Standard Operating Procedures (SOPs). Standard medical care (prophylactic, diagnostic and therapeutic procedures) remains in the responsibility of the treating physician of the patient.

The investigator should inform the sponsor immediately of any urgent safety measures taken to protect the study subjects against any immediate hazard, and also of any serious breaches of the protocol/ICH GCP.

The rights of the investigator and of the sponsor with regard to publication of the results of this study are described in the investigator contract. As a general rule, no study results should be published prior to finalization of the Study Report.

The protocol of this regulatory requisite PASS will be submitted to Saudi FDA for review and approval. This study will be conducted in accordance with the SFDA guidelines of good pharmacovigilance practice version 2.0.

████████████████████ will submit periodic reports as per SFDA guidelines of good pharmacovigilance practice version 2.0, and the final report to SFDA upon study completion. The periodic report for the final year will be substituted with the final report.

10.1 STUDY APPROVAL, PATIENT INFORMATION, AND INFORMED CONSENT

This study will be initiated only after all required legal documentation has been reviewed and approved by the respective Institutional Review Board (IRB) / Independent Ethics Committee (IEC) and Competent Authority (CA) according to national and international regulations. The same applies for the implementation of changes introduced by amendments.

Prior to patient participation in the study, written informed consent must be obtained from each patient (or the patient's legally accepted representative) according to ICH GCP and to the regulatory and legal requirements of the participating country. Each signature must be personally dated by each signatory and the informed consent and any additional patient-information form retained by the investigator as part of the study records. A signed copy of the informed consent and any additional patient information must be given to each patient or the patient's legally accepted representative.

The patient must be informed that his/her personal study-related data will be used by Boehringer Ingelheim in accordance with the local data protection law. The level of disclosure must also be explained to the patient.

The patient must be informed that his / her medical records may be examined by authorised monitors (CML/CRA) or Quality Medicine auditors appointed by Boehringer Ingelheim, by appropriate IRB / IEC members, and by inspectors from regulatory authorities.

